13.0 Risks to Subjects

- We anticipate minimal side effects and local irritation to be minimal. Muscle toxicity is a known adverse effect of statins. Patients will be notified during enrollment to watch out for common signs and symptoms such myalgias, fasciculations, cramping, myopathy and increased levels of CK. If an adverse event occurs, the subject must notify the study team members at their earliest convenience. Upon the subject's verbal notification to the study team, the study team will evaluate the adverse event and will proceed to document it and evaluate for subject safety. They will determine if subject is suitable to continue in the study.

- If there is an increased frequency of any concerning adverse event in particular, all enrolled participants in the trial will be sent an individual notice.
- There is a risk for possible breach of confidentiality as photographs of face may be taken to assess lesions on the head. However, all measures to keep information protected will be taken.
- There is a risk of emotional discomfort while the subject takes the questionnaires.
- A cumulative data assessment will be conducted every other month throughout the study's duration by study team members. A report that includes any available efficacy data, as well as a record of anticipated adverse events, will be compiled and submitted to the IRB at that time. Any event meeting the criteria of an unanticipated problem involving risks to subjects or others will be immediately reported to the MUSC IRB, as required by HRPP 4.7- Unanticipated Problems and Adverse Events Policy and Procedures.
- The plan for subject safety and minimizing risks of the research is as follows:
Inspection of the treatment site at each visit. Adverse effects of topical lovastatin/cholesterol will be specifically assessed at each research visit by the investigator, per outlined procedures. Participants are encouraged to reach out to the study coordinator if they think they are experiencing any adverse events. Other expected adverse effects deemed intolerable by the patient will prompt reduction in the patient's dose and treatment if indicated. Any condition necessitating cessation of the study drug will be followed to resolution.
- However, the side effect profile associated with both topical cholesterol and lovastatin is extremely small. We do not anticipate there being any complications associated with treatment other than minor, local irritation. The rare chance of developing stain induced myopathy and its associated signs and symptoms will be addressed during enrollment and each individual visit.

14.0 Potential Benefits to Subjects or Others

Patients will may benefit from the intervention. Researchers hope that the treatment will help clear active DSAP lesions, but all benefits are hypothetical currently.

15.0 Sharing of Results with Subjects

Results may be shared with subjects at the end of the study per verbal request.

6.2 Secondary outcomes	
7. Missing data	

1 Introduction

The aim of this study is to test in a single-center randomized clinical trial, if topical statins combined with topical cholesterol can reduce the severity (size, color, quality of life impact) of disseminated superficial actinic vs statin therapy alone.

This statistical analysis plan (SAP) will give more detailed descriptions of the endpoints in the study and the corresponding analysis.

2 Study Design

Patients with previous diagnosis of DSAP will be approached for informed consent as directed in sections 8.0 and 9.0 of the protocol. If the patient is eligible for the study, he or she will be randomly assigned to one of two groups, Group A (cholesterol/lovastatin) and Group B (lovastatin only). The patient will not be informed of which group they are in and will not be informed of what their study medication is, allowing single-blinding. Researchers will not be masked.

Enrolled subjects will be followed up at monthly intervals for three months via virtual check-in using an MUSC approved HIPAA compliant technology. At each visit, participants will undergo brief, limited physical examination (in order to determine disease severity and affected body surface area); additionally, clinical photographs of the lesion will be obtained in clinic or shared virtually with the investigators via secure email (sent to MUSC Outlook email). The physical exam will occur in-person or by using the virtual visit technology, which allows us to see the patient and visualize their skin findings. Photographs will be stored in the coded study-specific medical record for further analysis of lesion features.

At each visit a Patient Quality of Life, Physician Global Assessment Scale, and RAND36 will be administered.

Patients will be contacted via formal virtual visits at weeks 4, 8, and 12 and non-formal check-ins at weeks 2 and 6. Patients will be asked about compliance and any adverse effects experienced. Patients are also encouraged to contact [name] and/or [name] at any given point during the study if they think they are experiencing study-related side effects. Immediate consultation will follow to determine the severity of such event and necessary impacts on patient health and participation. Non-formal check-ins will be done over phone by study team member to assess for any adverse effects at weeks 2 and 6 of treatment.

Compounded topical medication prescribed to subjects will be self-applied twice daily. These medications will be prepared by Tidewater Pharmacy in Mount Pleasant, SC or Chemistry Rx in Philidelphia, PA dependent upon patient geography. They will be prepared so the study will remain single-blinded (only investigators know which study drug they are receiving) and associated costs will not be covered by the research budget. The cost of the medication will be approximately \$85 when dispensed by Tidewater Pharmacy,

1/12/22

or \$110 when dispensed by Chemistry Rx. The differences in costs are attributed to shipping and pharmacy fees.

Both pharmacies will be compounding the drugs to be used in this study, and the compounding formula (recipe) will be identical between these two compounding pharmacies.

Enrollment and prescription drug delivery to other states will not be performed until the respective state pharmacy boards confirm the legality of clinical telehealth interventions and out-of-state pharmacy prescriptions. All state and federal guidelines will be followed according to their regulations and recommendations.

Patient prescriptions will be called in to their respective pharmacies by credentialed study team members after enrollment is completed. Individual prescriptions will be called in to the aforementioned pharmacies so that the pharmacies can individually ship the medication to the respective participant. Both pharmacies are well aware of the study protocol and procedures for sending the prescription. This will occur by standard procedure of calling medications for patients:

- 1. The study team member will call the pharmacist to inform them that a participant has been enrolled and ready to receive one of the two single-blinded drugs. On the prescription label there will be a codename, application instructions, and storage instructions.
- 2. Per standard procedure of calling in a prescription, the study team member will verbally inform the Tidewater/Chemistry Rx pharmacist of the patient name, birthday, and phone number so that the medication can be prescribed and so that the patient can be contacted by the pharmacist for shipping and payment purposes.
- 3. The pharmacist will contact the patient over the phone in order to complete the medication payment over the phone and to identify the address to which the medication will be sent to.
- 4. The subject will inform the study team member upon receival of the medication, confirm that they received the correct, randomized medication.
- 5. All of the information related to drug disposal and reception will be recorded on the coded Drug Accountability Sheet, which is located separately in the secure box drive.

Medications will be able to be shipped to all continental US states by Chemistry Rx, except Alabama. This is because Chemistry Rx does not have the license to dispense to Alabama. Therefore, any participant reliant upon an Alabama address to receive their medication will not be allowed to participate in this study.

Dermoscopic and clinical photographs will be subsequently analyzed for the presence of cornoid lamella. The team will record any additional dermoscopic or clinicals feature that may arise during the analyses.

Frequency of dermoscopic and clinical features will be analyzed against clinical involution to find possible predictors.

Procedures during the day of imaging:

The doctor will identify the lesion(s) that will be analyzed.

The lesion(s) will be measured and clinical and dermoscopy photographs will be taken. Facial images might be taken to assess lesions on the head area.

Schedule of events:

Event	Screenin	Wee	Wee	Week
	g	k 4	k 8	12
	Baseline	(virt	(virt	(virtua
	Visit 1	ual)	ual)	1)
Informed	X			
consent	A			
Eligibility	X			
Assessment				
Demographics	X			
Physical	X			
Examination				
Clinical	X	X	X	
photograph &				X
Scale (3x)	71	11	71	71
administration				
Dermoscopic	X			
photograph	Λ			
Adverse events	X	X	X	X
monitoring				Λ

2.1 Sample Size Calculation

DSAP is a rare disease that effects people from a wide geographical region. The goal sample size for the study was to recruit 50 subjects, however, due to recruiting limitations and state regulations, we were only able to enroll 31 patients. No formal sample size calculation was necessary as this study is first of its kind.

3. Aims and Objectives

• The purpose of this study is to evaluate the effectiveness of cholesterol/lovastatin versus lovastatin alone to treat porokeratosis. Our working hypothesis is that both topical cholesterol/lovastatin and lovastatin alone are helpful in treating patients with disseminated superficial actinic porokeratosis (DSAP).

DSAP: Single-Blinded randomized trial

Aims:

- 1. To evaluate the response (lesion size, color, patient quality of life) to treatment with topical cholesterol/lovastatin and lovastatin alone in a series of patients with the diagnosis of DSAP.
- 2. To characterize lesion patterns following topical treatment and patterns of lesion regression.
- 3. Access quality of life outcomes through RAND36 and DLQI surveys.

4. Outcomes

This section will present the outcomes investigated to answer the study aims and objectives. The analyses are described in section 6 Analyses.

4.1 Primary outcome

Percentage of lesion clearance after 12 weeks of therapy using an exploratory clinical measure modified from a validated psoriasis index. The Disseminated Actinic Porokeratosis General Assessment Severity Index (DSAP-GASI) included plaque/rim elevation, scaling, and color (0= clear, 1=almost clear, 2=mild, 3=moderate, and 4=severe).

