4.0 Study Endpoints

- Percentage of clearance of disseminated superficial actinic porokeratosis lesions after 12 weeks of therapy
- Validated scale changes: Patient Quality of Life (RAND36, DLQI), Physician Global Assessment Scale (DSAP-PGA), Actinic Keratosis Field Assessment Scale
- Clearance of coronoid lamella on dermoscopy (or photograph) after 12 weeks of therapy.

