11.0 Data Management

- Continuous data will be summarized using descriptive statistics (number of values, means, standard deviation, median, minimum and maximum). Categorical data will be summarized using frequency tables (frequencies and percent).

- We are comparing before and after photographs from the same patient, hence we employ analysis by paired t-test to compare baseline data with data after treatment.
- Coded dermoscopic and clinical photographs may be obtained for further analyses. Files with patient images will be stored in a secure departmental drive that will only be accessible to study team members by their unique MUSC ID and password.
 - Photos shared directly via email to study team members will be also be uploaded to the participants respective coded folder on the Box drive.
 - These emailed photos (sent by the participant personal email) must be de-identified close up photos of the participants legs or arms, and sent only to study team members secure MUSC-assigned Outlook email addresses. Photos that do not fit this criteria will be deleted upon receipt and not used in the study.
- All subject medical record information and data collection will be coded and stored on an MUSC Box drive only accessible to study team members, and will be protected by two-factor authentication.

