6.1 Primary outcome

The primary analysis will compare the improvement in DSAP-GASI scores before treatment and after treatment in both groups. Only participants with clearly documented photos across all visits will be considered for the DSAP-GASI efficacy analysis. The scores will be graded by two blinded, trained physicians. Cronbach's Interrater reliability will be calculated among raters across visits and the scores will be averaged for each of the four visits. Overall efficacy will be examined using a 2X4 (Drug X Time) Repeated Measures Analyses of Variance (ANOVA). The statin/cholesterol vs statin groups will be compared and evaluated for significant differences

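### The primary outcome is named as a clearance percentage at week 12, but the SAP gives no rule for deriving one from DSAP-GASI grades and does not say which ANOVA term or contrast is decisive

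*SAP*

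**What the plan says.** Protocol 4.0 lists first, without ranking its endpoints, "Percentage of clearance of disseminated superficial actinic porokeratosis lesions after 12 weeks of therapy". It gives no formula.

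SAP 4.1 makes this the primary outcome: "Percentage of lesion clearance after 12 weeks of therapy using an exploratory clinical measure modified from a validated psoriasis index". Its next sentence identifies the measure as DSAP-GASI, which covers plaque or rim elevation, scaling and color on a scale from 0 (clear) to 4 (severe).

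SAP 6.1 describes the analysis: "The primary analysis will compare the improvement in DSAP-GASI scores before treatment and after treatment in both groups". Two blinded physicians grade the photographs, and "the scores will be averaged for each of the four visits". The model is a 2 by 4 (Drug by Time) repeated measures ANOVA, followed by a statement that the two drug groups will be compared for significant differences. The analysis set is restricted: "Only participants with clearly documented photos across all visits will be considered for the DSAP-GASI efficacy analysis".

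Protocol 11.0 names a different method, a paired t-test of baseline against post-treatment data within the same patient.

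**The concern.** A primary outcome should be a quantity that the primary analysis estimates. Here the name is a percentage of lesions cleared at one time point, while the analysis is of mean severity scores over four. The step between them is missing, so whoever reports percentage clearance has to choose its definition at that stage.

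The second gap is the test. A Drug by Time ANOVA produces three omnibus tests (Drug, Time, and Drug by Time), and SAP 6.1 does not say which one, or which contrast, answers the primary question. The surrounding text points two ways. The working hypothesis in SAP 3, that both treatments help, and the before-and-after wording of 6.1 suggest change over time. The aim in SAP 1, the combination against statin alone, and the last sentence of 6.1 suggest a difference between arms. The protocol's paired t-test adds a third candidate. What is at stake is whether the statement made about efficacy was fixed by the plan or depends on which line of output is read.

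**Working it through.** The plan states no figure to reproduce: there is no significance level, effect size, standard deviation or sample size calculation. The check sets the sections side by side and then uses illustrative numbers, marked as assumptions.

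**1. From grade to clearance percentage.** Four things are needed: whether the 0 to 4 grade is given per feature or overall, how the features combine, how several lesions in a participant combine, and what counts as clearance. SAP 4.1 gives only the features and the grade labels. SAP 2 allows more than one lesion to be identified for analysis. SAP 6 to 7 contain no clearance calculation. Protocol 11.0 offers frequency tables in general terms. None of the four is settled.

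**2. Does the mean score determine clearance?** Two readings of the term are open.

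- *Share graded clear.* Assume one grade per participant, both raters agreeing, and everyone at 3 at baseline. A week-12 mean of 1.0 arises in three ways:
  - all graded 1: mean 1.0, 0% clear;
  - half at 0 and half at 2: (0 + 2)/2 = 1.0, 50% clear;
  - three-quarters at 0 and one-quarter at 4: 0.75 × 0 + 0.25 × 4 = 1.0, 75% clear.
- *Percent reduction from baseline.* In all three cases the reduction is (3.0 − 1.0)/3.0 = 67%, so that example does not separate them. A change in score still does not fix the percentage. If the features were summed to 0–12 (an assumption), a 2-point fall is 2/4 = 50% from 4, 2/8 = 25% from 8 and 2/12 = 16.7% from 12. None of these ends at clear.

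**3. Which term?** Let d be the between-arm difference at week 12, with randomised arms expected to be equal at baseline. The Drug main effect is the average of the differences at weeks 0, 4, 8 and 12:

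- linear growth: (0 + 1/3 + 2/3 + 1)d/4 = 0.50d;
- difference at week 12 only: (0 + 0 + 0 + 1)d/4 = 0.25d;
- complete by week 4: (0 + 1 + 1 + 1)d/4 = 0.75d.

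The baseline-to-week-12 contrast is d − 0 = d in each case.

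A simulation of 20,000 runs shows the consequence. It assumes 16 and 15 participants (all 31 enrolled), SD 1, between-visit correlation 0.5 or 0.7, and a two-sided 5% level.

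- Arms identical, both improving by 0.8 SD by week 12: Time is significant in 98% to 100% of runs; Drug and Drug by Time in about 5% each.
- Difference growing linearly to 0.8 SD: power is 22% to 28% for Drug, 47% to 70% for Drug by Time, and 58% to 80% for a t-test of change to week 12.

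**4. Precision of a clearance comparison.** Assume 10 to 15 assessable participants per arm, one yes/no result each, and the same proportion p clear in both arms. With Wilson limits l and u, the Newcombe 95% half-width is taken as √[(p − l)² + (u − p)²]. For 2/10 in each arm, l = 0.057 and u = 0.510, giving √(0.143² + 0.310²) = 34.1 points. Likewise 5/10 gives 37.3, 3/15 gives 28.3 and 8/15 gives 31.9.

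**The case against.** The strongest reply is that SAP 4.1 and 6.1 use the same instrument and that 6.1 names a single model. Both statements are true, and they rule out several stronger readings.

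- *A reader might infer that the SAP swaps its primary outcome for an unrelated measure.* It does not. SAP 4.1 itself names DSAP-GASI. What is missing is the conversion rule, and whether the named outcome goes wholly unestimated depends on what clearance was meant to be.
- *A reader might infer that no primary test exists.* One model is named, and comparing improvement between groups leans towards Drug by Time, not towards the Drug main effect to which the dilution applies. That is a sensible inference, but 6.1 does not state it, and even the overall interaction is not targeted at week 12.
- *A reader might take 0%, 50% and 75% as the size of an error.* They show ambiguity only. They apply if clearance means graded clear, and the third case needs a quarter of participants to worsen from 3 to 4.
- *A reader might infer a false-positive risk of 1 − 0.95³ = 14.3% from three tests.* That would require any significant line to count as success. The plan states neither such a rule nor a significance level.
- *A reader might infer that the outcome was shaped by the results.* SAP 2.1 reports enrolment of 31 as complete and researchers are unmasked, but the photograph graders are described as blinded, and nothing says outcome data had been seen.

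It could also be said that the protocol's endpoint "Clearance of coronoid lamella on dermoscopy (or photograph) after 12 weeks of therapy" supplies a percentage. It is a separate endpoint and is not the SAP's primary outcome.

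Finally, the measure is labelled exploratory and the trial is small. That argues for modest claims, but it does not remove the need to say what is being estimated.

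**Conclusion.** The point stands in this form: the primary outcome is named as a clearance percentage at week 12, no rule derives it from DSAP-GASI, and the ANOVA as written does not produce it. A result on mean scores cannot be reported as clearance if that means graded clear. One model is named without a decisive term or week-12 contrast, and Protocol 11.0 names a different, within-patient test.

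The size is conditional. The factors 0.25 to 0.75 are arithmetic, given equal arms at baseline and the three time courses shown, and they concern the Drug main effect only. The power figures and the clearance percentages rest on assumed values and serve as illustration. Choosing the baseline-to-week-12 contrast over the overall interaction is a recommendation, because it matches the stated time point; the documents do not require it.

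**What to change.** In SAP 4.1 and 6.1:

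- Name the analysed primary outcome as change in DSAP-GASI score from baseline to week 12. State how the three features and several lesions per participant are combined.
- Make the between-arm difference in that change (the baseline-to-week-12 Drug by Time contrast) the single primary test. Keep the four-visit ANOVA and the protocol's paired t-test as supportive.
- Do not label score change as clearance.
- Report clearance separately by arm from the existing blinded grades, as the percentage of assessed lesions graded clear at week 12. If there is only one grade per participant, report the proportion of participants clear and label it so. Give a 95% confidence interval for the difference that allows for several lesions in one participant.
- Because the SAP's wording shows enrolment already complete and researchers are unmasked, record the change as an amendment and state whether outcome data had been seen.

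The cost is SAP wording and a small tabulation, provided the raters' individual grades were kept. The drawback is imprecision: about plus or minus 28 to 37 points for the clearance difference under the participant-level assumptions above. A lesion-level interval would also depend on lesion counts and within-participant correlation, which the documents do not give. The clearance comparison should be presented as descriptive.

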4.2 Secondary outcomes

Self-reported evaluations (better, unchanged, worse) on overall appearance, color, scale, pain, and itch. Application frequency and consistency along with safety and tolerability were also assessed at each visit.

Surveys: Patient quality of life measures, DLQI, and RAND36

4.3 Safety Outcomes

Adverse events

Adverse events are reported at each clinic visit. Patients are also encouraged to contact [name] and/or [name] at any given point during the study if they think they are experiencing study-related side effects. Immediate consultation will follow to determine the severity of such event and necessary impacts on patient health and participation. Participants will also be contacted by phone by study team member to assess for any adverse effects at weeks 2 and 6 of treatment.

5. Populations and subgroups to be analyzed

5.1 Populations

Intention-to-treat (ITT)

All randomized study subjects.

Per Protocol (PP)

All randomized study subjects completing the whole study period (complete cases). For a specific analysis, study subjects with missing data on any of the variables in the model will be excluded from the analysis. Analyses of this population is seen as a sensitivity analysis to investigate whether conclusions are sensitive to assumptions regarding the pattern of missing data.

6. Analysis

All enrolled subjects are considered in the demographic data and safety analysis. Treatment efficacy is based on investigator-standardized patient-documented photographs. Repeat photo documentation will be obtained if image quality was inadequate or angle, lighting or location is not standardized to prior photos.

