- Compounded topical medication prescribed to subjects will be self-applied twice daily. These medications will be prepared by Tidewater Pharmacy in Mount Pleasant, SC or Chemistry Rx in Philadelphia, PA. They will be prepared so the study will remain single-blinded (only investigators know which study drug they are receiving) and associated costs will not be covered by the research budget. The cost of the medication will be approximately \$85 when dispensed by Tidewater Pharmacy, or \$110 when dispensed by Chemistry Rx. The differences in costs are attributed to shipping and pharmacy fees.
- Both pharmacies will be compounding the drugs to be used in this study, and the compounding formula (recipe) will be identical between these two compounding pharmacies.
- Enrollment and prescription drug delivery to other states will not be performed until the respective state pharmacy boards confirm the legality of clinical telehealth interventions and out-of-state pharmacy prescriptions. All state and federal guidelines will be followed according to their regulations and recommendations.
- Patient prescriptions will be called in to their respective pharmacies by credentialed study team members after enrollment is completed. Individual prescriptions will be called in to the aforementioned pharmacies so that the pharmacies can individually ship the medication to the respective participant. Both pharmacies are well aware of the study protocol and procedures for sending the prescription. This will occur by standard procedure of calling medications for patients:
 - 1. The study team member will call the pharmacist to inform them that a participant has been enrolled and ready to receive one of the two single-blinded drugs. The lovastatin/cholesterol combination has been assigned the arbitrary codename “RDC100”, and the lovastatin alone medication has been assigned the arbitrary codename “RDC15”. On the prescription label there will be the codename, application instructions, and storage instructions.
 - 2. Per standard procedure of calling in a prescription, the study team member will verbally inform the Tidewater/Chemistry Rx pharmacist of the patient name, birthday, and phone number so that the medication can be prescribed and so that the patient can be contacted by the pharmacist for shipping and payment purposes.

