 - 3. The pharmacist will contact the patient over the phone in order to complete the medication payment over the phone and to identify the address to which the medication will be sent to.
 - 4. The subject will inform the study team member upon receipt of the medication, confirm that they received the correct, randomized medication.
 - 5. All of the information related to drug disposal and reception will be recorded on the coded Drug Accountability Sheet, which is located separately in the secure box drive.

- Medications will be able to be shipped to all continental US states by Chemistry Rx, except Alabama. This is because Chemistry Rx does not have the license to dispense to Alabama. Therefore, any participant reliant upon an Alabama address to receive their medication will not be allowed to participate in this study.
- Dermoscopic and clinical photographs will be subsequently analyzed for the presence of cornoid lamella. The team will record any additional dermoscopic or clinical feature that may arise during the analyses.
- Frequency of dermoscopic and clinical features will be analyzed against clinical involution to find possible predictors.
- Procedures during the day of imaging:

The doctor will identify the lesion(s) that will be analyzed.

The lesion(s) will be measured and clinical and dermoscopy photographs will be taken. Facial images might be taken to assess lesions on the head area.

Schedule of events:

Event	Screening Baseline Visit 1	Week 4 (virtual)	Week 8 (virtual)	Week 12 (virtual)
Informed consent	X			
Eligibility Assessment	X			
Demographics	X			
Physical Examination	X			
Clinical photograph & Scale (3x) administration	X	X	X	X
Dermoscopic photograph	X			
Adverse events monitoring	X	X	X	X

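### The safety analysis takes all enrolled subjects and no treated set is defined, so drug-related adverse event rates may be diluted if some subjects never used the ointment

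*SAP*

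**What the plan says.** SAP section 6 sets one rule for demographics and safety together: "All enrolled subjects are considered in the demographic data and safety analysis". It attaches no condition on receiving or applying the drug.

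SAP 5.1 defines two populations. The intention-to-treat set is "All randomized study subjects". The per-protocol set is the randomised subjects who complete the study with complete data. Neither depends on exposure, and no safety or treated set appears elsewhere in the SAP. SAP 6.2 adds only that application frequency and safety may be evaluated. SAP 2.1 gives the number enrolled: "we were only able to enroll 31 patients".

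The supply chain is described in Protocol section 10 and repeated in SAP section 2:
- "Patient prescriptions will be called in to their respective pharmacies by credentialed study team members after enrollment is completed".
- The ointment costs about $85 or $110 depending on the pharmacy, and "associated costs will not be covered by the research budget".
- "The pharmacist will contact the patient over the phone in order to complete the medication payment over the phone".
- After shipment, "The subject will inform the study team member upon receipt of the medication", and receipt is logged on the Drug Accountability Sheet.
- The ointment is self-applied twice daily.

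SAP 4.2 says that application frequency and consistency are assessed at each visit.

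**The concern.** Several steps lie between enrolment and first exposure: the prescription call, the patient's payment, delivery or pick-up, and self-application. A subject can stop at any of them and still count as enrolled. Such a subject cannot have a reaction to the ointment but stays in the safety denominator under SAP section 6.

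The protocol names local irritation and statin-type muscle symptoms as the risks to watch (sections 3 and 13). Section 13 also provides for a notice to all participants if a concerning event becomes more frequent, and for regular cumulative reports to the IRB. Frequencies that include never-exposed subjects could understate what users experience. If non-use is unequal between the arms, a safety comparison of the two products could show a difference that is not real, or hide one that is. SAP 4.3 places the safety phone calls at weeks 2 and 6 of treatment, a time scale that does not exist for someone who never started.

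**Working it through.** The plan states no adverse event rate, no safety denominator formula and no count of never-exposed subjects, so there is no figure to reproduce. The check is the size of the dilution under stated assumptions.

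**Inputs**
- N = 31 enrolled (SAP 2.1).
- k = enrolled subjects never exposed. This is not in the documents; the range 0 to 8 is assumed.
- Events are first assumed to occur only in exposed subjects, as for a drug reaction.

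**Dilution.** Rate over all enrolled = rate in users × (31 - k)/31.

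| k | Users | Factor | 3 events: of 31 / of users | 6 events: of 31 / of users |
|---|---|---|---|---|
| 0 | 31 | 1.000 | 9.7% / 9.7% | 19.4% / 19.4% |
| 1 | 30 | 0.968 | 9.7% / 10.0% | 19.4% / 20.0% |
| 3 | 28 | 0.903 | 9.7% / 10.7% | 19.4% / 21.4% |
| 5 | 26 | 0.839 | 9.7% / 11.5% | 19.4% / 23.1% |
| 8 | 23 | 0.742 | 9.7% / 13.0% | 19.4% / 26.1% |

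Each never-user lowers the rate by 1/31, about 3% relative. At k = 5 the loss is 5/31, about 16%.

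**Event never seen.** The exact one-sided 95% upper bound is 1 - 0.05^(1/n): 9.2% for n = 31, 9.5% for n = 30, 10.1% for n = 28, 10.9% for n = 26 and 12.2% for n = 23.

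**Arm comparison.** As an illustration, take arms of 16 and 15 and a true rate of 20% among users of either product.
- Five never-users, all in the arm of 15: 0.20 × 16/16 = 20.0% against 0.20 × 10/15 = 13.3%.
- Five never-users, all in the arm of 16: 0.20 × 11/16 = 13.8% against 0.20 × 15/15 = 20.0%.

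The apparent difference is created by non-use alone, and its sign follows the arm with more never-users.

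**Background events.** Now let never-exposed subjects also report m events unrelated to the drug, with x events among users. The all-enrolled rate is (x + m)/31, which is below x/(31 - k) only when m/k is less than x/(31 - k). With x = 6 and k = 5, the user rate is 23.1%. One background event gives 7/31 = 22.6%, still lower; two give 8/31 = 25.8%, which is higher.

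**The case against.** The strongest reply is that the effect may be nil. A reader might infer that the rates are in fact diluted, but no document reports a single subject who failed to buy or apply the ointment. If all 31 used it, the all-enrolled set and the treated set are the same. This stands, and the point is limited to what may happen.

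A reader might also infer that any bias must make the drugs look safer. That is not supported. SAP 4.3 does not limit adverse events to drug reactions, and the schedule monitors them from baseline, so an unexposed subject can contribute a background event. Between arms, the direction can go either way.

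The effect is also small beside the sampling error. For 3 events in 31 the exact 95% interval is 2.0% to 25.8%, while five never-users move the estimate only from 9.7% to 11.5%. This stands for the pooled rate, but it is no reason to leave the denominator wrong when correcting it is cheap.

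The SAP plans no explicit adverse event rate or between-arm safety test, so reading 31 as the divisor is an inference. It is a reasonable one, since the sentence in section 6 is the only rule on who enters the safety analysis.

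SAP section 7 excludes missing data from analysis, which might remove a never-starter who leaves without follow-up. That section does not mention exposure, does not clearly override section 6, and would not remove a never-starter who keeps attending visits.

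Finally, prescreening, the state-by-state legality check, the Alabama exclusion and confirmation of receipt make non-receipt less likely or easier to detect. They do not decide who is in the safety set.

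**Conclusion.** The point holds as a gap in the plan, not as a demonstrated bias. SAP section 6 places all enrolled subjects in the safety analysis, SAP 5.1 offers no treated set, and the patient-paid supply after enrolment makes an enrolled but unexposed subject plausible. For drug-related events the dilution factor is (31 - k)/31: none at k = 0, about 3% relative per never-user, and about 16% at k = 5. The value of k is an assumption throughout. For events of any cause a lower rate is likely but not certain, and unequal non-use could distort the arm comparison in either direction.

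Protocol section 16 has the drug compounded before the week 0 visit, while section 10 has the prescription called in after enrolment. These should be reconciled. The point does not depend on which holds: under section 16 the ointment still waits at the pharmacy for pick-up or delivery, and neither section ties the safety set to use.

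**What to change.** In SAP 5.1, add a safety set and refer to it in section 6:
- **Definition:** randomised subjects with at least one application of study ointment, grouped by product received.
- **Uncertain application:** a subject who received the ointment stays in the set unless non-application is confirmed. This covers someone who has the drug but is lost before reporting on its use.
- **Data:** the receipt information on the Drug Accountability Sheet and the application-frequency answers collected at visits. The documents do not say that a date of receipt is recorded, so the definition should not depend on one.
- **Reporting:** state the denominator for adverse event rates and give the number never exposed in each arm.
- **Demographics:** keep all enrolled subjects.

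This takes a short SAP amendment and no new data collection. The costs are slightly smaller denominators and reliance on self-reported application. If every subject used the ointment, the results do not change.
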